Collection of morbidity data:

Morbidity information will be collected at two weekly home visits during study period using pre-tested questionnaire.

Operational definition

Fever: If the temperature is more than normal, that is above 38.5⁰ C is called fever.

In the field level:

1. When mother tell about her child suffered from fever that lasted for 1 day, a physician will examine the child and child will be treated at home for mild fever.
2. When mother will tell that her child has fever lasting for two to three days, it will be regarded it as moderate fever.
3. Mother will tell that fever lasts for more than three days, he will be examined and regarded as sever fever.

Diarrhoea: An episode of diarrhea is defined as the passage of three or more loose or watery stools within 24 hours. Records will be collected on consistency and the number of stools per day.

1. A child passing loose, liquid or watery stool more than three times per day will be called acute diarrhoea.
2. Presence of blood with stool will be define as invasive diarrhea.
3. When a single episode of diarrhea lasts for more than two weeks, it will be called persistent diarrhoea.

Ear Infection: A child will have pain in ear, fever, with watery or purulent secretion from one or both ear will be diagnosed as ear infection.

Lower respiratory tract infection: When a child suffering from cough and fast breathing more than 50 per minute, fever, or chest indrawing will be defined to have lower respiratory tract infection (LTRI).

Upper respiratory tract infection: A child suffering from cough and cold without sings of LRTI will be diagnosed as upper respiratory tract infection (URTI).

Skin infection: A child suffering from skin disease with impetigo or skin infection or scabies will be define have skin infection.

Sore on Tongue: Ulceration or fissure on tongue or palate will be identified as sore tongue.

Angular stomatitis: Any child having signs of ulceration or excoriation in angle of mouth will be diagnosed to have angular stomatitis.

Xerpthalmia : Conjuntival haziness & corneal haziness will be diagnosed as Xerophthalmia.

The subjects will be referred to THC by interviewers during two weekly home visits if following conditions develop:

Referral will be done accordingly to IMCI criteria in the following ways:

1. Pneumonia: After 2 days of first time of antibiotic therapy:

Check the child for general danger signs.

Assess the child for cough or difficult breathing.

Ask:

- Is the child breathing slower?
- Is there less fever?
- Is the child eating better?

Treatment:

- If chest indrawing or a general danger sign, give a dose of second-line antibiotic or intramuscular chloramphenicol. Then refer URGENTLY to THC.

2. Diarrhoea:

After 5 days:

Ask:

- Has the diarrhoea stopped?
- How many loose stools is the child having per day?

Treatment:

- If the diarrhoea has not stopped (child is still having 3 or more loose stools per day), do a full reassessment of the child. Give any treatment needed. Then refer to THC.

3. Dysentery:

After 2 days:

Ask:

- Are there fewer stools?
- Is there less blood in the stool?
- Is there less fever? Is there less abdominal pain?
- Is the child eating better?

Exceptions- If the child:

- is less than 12 months old, or
- was dehydrated on the first visit, or
- had measles within the last 3 months. Then refer to THC.

4. Ear-Infection:

After 5 days:

Ask:

- Is there ear pain?
- Is there ear discharge? If yes, for how long?

Look and feel:

- Look for pus drawing from the ear.
- Feel for tender swelling behind the ear.

Treatment:

- If there is tender swelling behind the ear or high fever (38.5°C or above), refer Urgently to THC.

5. Fever:

Ask:

- For how long?
- If more than 7 days, has fever been present every day?
- Has the child had measles within the last 3 months?

Look and feel:

- Look or feel for stiff neck.
- Look for runny nose

Look for signs of measles

- Generalized rash and
- One of these: cough, runny nose, or red eyes.

Treatment:

- Very severe febrile (high fever 38.5°C for above), then refer urgently to hospital.
- If fever is present every day for more than 7 days, refer for assessment.

Qualitative data collection methods

The baseline data will be collected through:

1. Survey
2. Focus group discussion
3. Participant observation:

Each method of data collection is elaborately mentioned bellow.

1. **Survey:** Information of socio economic condition of the respondents will be collected through direct questionnaire. These answers will cover the issues of family income, food status, education, occupation of the parents and also the size and type of the family.

2. **Participant Observation:** Participant observation will be conducted to explore basic feeding

pattern at home like breast feeding frequency, complimentary feeding, frequency of feeding, gender bias on feeding practice and allocation of time for child care. Anthropologist or nutritionist will observe 10-15 mothers of moderately malnourished children. Mothers will be observed from morning till evening. Data collected through participant observation will validate the data of focus group discussion.

3. Focus group discussion (FGD):

It is necessary for the immediate care givers of children, mothers or guardians to be involved in the problem and to initiate remedial measures with the help of their own resources that they can obtain from their environment. From FGD of mothers and caregivers we expect to learn and use information to develop appropriate culturally based practical nutrition education messages for the following issues:

1. Perceptions on causes and possible consequences of malnutrition from mothers that they experience in their day to day life.
2. Ideas on the management of the nutritional problem and its preventive measures.
3. The perceptions on food security.
4. Feeding practice of children and pattern and frequency of breast-feeding.
5. Mothers' perceptions about initiation of immunization.
6. Mothers beliefs on foods for child health, feeding requirement and appropriateness of food.
7. Food taboos and practices in diseases.
8. Perceptions and practices on healthy food and non-healthy food at different ages of a child.
9. Perceptions on growth and their responsibility on caring practice and complementary feeding.

The views expressed by the mothers through Focus Group Discussion on possible causes of malnutrition and their suggestion on the preventive and management measures will be used as base line data to prepare the material for counseling mothers on nutrition related behavior change.

FGD will be conducted on mothers in 6 groups each from 3 CNC's (1 control and 2 study areas). There will be 6-8 mothers of moderately malnourished children in each Focus Group Discussion. This is expected to be more or less homogenous, since mothers having young children in the villages are of similar age FGD will be conducted by the anthropologist. Moderator will play the role of guiding the group on the right topic by putting them on the track. The research personnel will facilitate discussion but they will not influence the discussion. A tape recorder will be used to record the discussion. One facilitator will take notes. Obtained data from FGD will be analyzed manually by using coding.

The FGD will be conducted again to evaluate the change in behaviour and the process indicators. The method indicated above will be followed in the later part of the study.

A pre-test on knowledge of child feeding practice will be done and will be repeated with same the questionnaire after the diet counselling sessions with the mothers. Data on feeding frequency, preparation of information on child feed, dietary ingredients, frequency of feeding and constraints will be recorded at two weekly intervals in study groups. Post test will be conducted at the end of

nutrition education period.

The health assistants will be pre-testing the nutrition knowledge of the mothers and mothers will be observed before actual training is given. These subjects will not be included into study. This will reduce observer bias of the health assistants.

Outcome variables:

1. Mothers understanding and ability to identify moderate malnutrition in children.
2. Mothers understanding on consequence of moderate malnutrition.
3. Change in knowledge of mothers in feeding practices.
4. Frequency of home feeding (Breast-feeding and supplementary feeding).
5. Frequency of seeking medical care during illness, referral, incidence, duration of illness.
6. Adequacy of child feeding, frequency & type of feeding.
7. Weight gain, weight for age and weight for height at the end of intervention.
8. Proportion of complementary feeds in 6-9 months age group.
9. Nutritional status of children at various phases of intervention and observation.
10. Adaptation level of nutrition education program by CNP, CNO.
11. Constant of not practicing education knowledge.

Secondary outcome variables: -

1. Incidence and prevalence of diarrhoea and ALRI
2. Referral success and failure
3. Resistance to education
4. Food insecurity for child
5. Mothers time constraint for CF preparation
6. CNP time constraints for INE

Process indicators:

5. Number of counseling sessions
6. Proportion of attendance by mothers to counseling session
7. Proportion of attendance of supplementary feeding demonstration session
8. Number of home visits of by Health assistants
9. Use of IEC materials in sessions.
10. Number of community sessions with mothers groups, women's group, and VNMC.
11. Proportion weighing sessions.
12. Member of VNMC meetings.
13. Percent of feeding frequency change.
14. Record of referral.
15. Feeding related behaviour.

Quality control measures:

Quality assurance will include questionnaire development, FGD, intensive staff training, standardization of study procedures, which will be written in detailed manuals, regular staff meetings and supervision by the investigators. The project investigators in 15% random samples will directly supervise systematic data collection. Anthropometry will be standardized at the beginning of monthly sessions by trained nutritionist. External validation of anthropometry will also be done. Validation of nutrition education will be done by attending the sessions by supervisors during group with a check list education and with separate interview. Cross check with mothers for preparation of feeds and feeding frequency will be done by nutritionist. Feeding frequency will be rechecked after the day of interview in 15% of the randomly selected sessions at the household levels. Investigators will make random spot checks and will re-interview at least 15% of mothers on child morbidity on the same day using the same questionnaire. With identification of any discrepancy, the data will be informed to the respective health workers and corrections will be done by supervisor's assistance. Each child will have a record file of important events such as migration, referral, and death and will be kept with project office. The field activity will be communicated to PI by the project supervisors and senior staff by phone or fax in between the visits in the field. Data will be checked by running checking program in computer after collection and before analysis.

Adaptation process of the Community Nutrition Promoters (CNP's) and Community Nutrition Organizer (CNO's):

CNP and CNO's will be asked for their time to learn the specific nutrition education that has proven to be successful for improving nutrition status and they will be involved to pick up the work schedules of the research team. After the first three months of study, adaptation process will begin. If time is available CNP's will take over the health assistant's work and CNO's will take over supervisor's work by end of 6 months and will replicate in more CNC's.

Time will be planned with CNO and CNP's to define their role in nutrition education. The current

study with knowledge of the previous one will identify specific knowledge base that helps behavior change communication of mothers in feeding appropriate food and frequency, referral during illness, and caring practices. A review of the BINP training manual will be done to find adjustment of the specific messages based on our messages on the preventive and management approaches for introduction of complementary feeding. An initial standardization of CNP sessions with mothers will be done with project investigators and field staff. Supervisory level adaptation of monitoring the quality of CNP and CNO work will be planned and accommodated. It remains to see the actual operations taking place in context of time constraint of CNP's in their daily work schedules. The details on following areas will be worked out with the NGO implementing in Thanas before planning of adaptation can be actually begun.

1. Availability of CNP and CNO time
2. Training of CNP and CNOs
3. Monitoring / Supervision
4. Evaluation of the work

Cost Effectiveness of the Alternative Strategies to address moderately malnourished children

Add in specific objective section the following:

5. To assess the cost-effectiveness of the two alternative strategies to prevent and reduce moderate malnutrition in 6-24 months old children.

Add in the conceptual framework section:

In order to assess the cost-effectiveness of the two alternative strategies, the costing of the intervention activities will be undertaken.

To ensure that all relevant resources used for the alternative intervention strategies, it will be necessary to observe outputs (effectiveness measures) being produced and then try to link the inputs/resource used in the production of specific outputs.

Data will be collected to determine the following costs while undertaking the intervention.

The costing will be done from providers'/programme perspective and will include the identification of the following:

Capital costs will include values of setting up (building, furniture, equipment, vehicles), and training (non-recurrent). *Recurrent costs* will include personnel (salaries and benefits), training (recurrent), rent and utilities, equipment and supplies (operation and maintenance), building (operation and maintenance), vehicle (operation and maintenance), head office (HO) logistic and management support, and supervision (HO and regional quality control). Attempts will be made to identify the

cost, which are only the research components. The incremental costs of adopting the alternative strategies will be analyzed.

Relevant data for this part of study will be collected simultaneously with the main part of study. Additional tools will be developed to collect data.

The emphasis of the economic evaluation through cost-effectiveness analysis will be to evaluate the direct and indirect cost for each type of output measures. The main indicators of effectiveness (output) measures will include:

- proportion of mothers understanding the consequences of moderate malnutrition
- proportion of mother with improved knowledge in feeding practices
- proportion of child with improved nutritional status at various phases of intervention

Add in the personnel requirements:

This part of the activity will include involvement of one Senior Operations Researcher and Senior Field Research Assistant from the Health Economics Program. It is suggested that about 10% of Senior Operations Researcher's time will be needed for 18 months. He/she will mainly provide the guidance in designing the data collection instrument and analyzing the data. A full time Senior Field Research Assistant for 12 months, who will report to the Senior Operations Researcher of the Health Economics Programme, will be needed to supervise the field data collection and the interviewers to be assigned for collecting cost information.

Facilities Available

Describe the availability of physical facilities at the place where the study will be carried out. For clinical and laboratory-based studies, indicate the provision of hospital and other types of patient's care facilities and adequate laboratory support. Point out the laboratory facilities and major equipment that will be required for the study. For field studies, describe the field area including its size, population, and means of communications. (TYPE WITHIN THE PROVIDED SPACE).

Site selection:

This research project will be conducted in 4 thanas in four Divisions, one in Khulna, one in Dhaka, one in Rajshahi and the other in Chittagong. Four thanas that are under CBNC activities will be randomly selected from each division. These are NGO run thanas where the NGO's are implementing the project activity with the help of Government or vice versa in the Government run thana. Then eight unions will be selected from these four thanas. That means two unions will be selected from each thana by using simple random sampling. Again by using simple random sampling six CNC's (Community Nutrition Centre) will be selected from each union. The basic information, already existing in the registrar (e.g. anthropometry) of the CNP will be reviewed.

Data Analysis

Describe plans for data analysis. Indicate whether data will be analyzed by the investigators themselves or by other professionals. Specify what statistical software packages will be used and if the study is blinded, when the code will be opened. For clinical trials, indicate if interim data analysis will be required to monitor further progress of the study. (TYPE WITHIN THE PROVIDED SPACE).

Data will be double entered in a microcomputer within a week of data collection. The field supervisors will visually check data before sending for entry into the computer. Any error, discrepancy or omission found during data entry will be reported to the investigators without delay. Data will be entered into microcomputer using SPSS Windows's program. Data on weight gain, frequency and introduction of complementary feeding will be compared between experimental groups. Complementary feed introduction and regularity will be compared among 6-9 month age groups in education and control groups. Comparability between intervention and control groups will be assessed by baseline characteristics such as age sex, nutritional status, socioeconomic characters, feeding practices, etc. Continuous variables will be assessed for normal distribution. T test will be performed to compare data of normal distribution; otherwise non-parametric test will be used. Chi-squared test will be performed for categorical variables, Multiple regression analysis will be done with weight gain as dependent variable and intervention and potential confounding variables such as age, sex, SES, baseline nutritional status, infection as independent variables. Separate analysis will be performed for periods of intervention, reinforcement and observation.

Compliance of nutrition education will be measured at 2 weekly observation period (already mentioned). Compliance will be measured as process indicator. Comparison of compliance will only

be done at the end of the study so that the investigators will have no idea about which group is more a less compliant. Therefore, these will be little change of introduction of bias due to non-compliance, effect of intensive or less intensive nutrition education will be compared as a whole. So complain will be seen as a factor of nutrition education with given intensive. Analysis of compliance data will be done by relating to the outcome effect of nutritional status and can be compared between two education groups.

Analysis of qualitative data

Data collected from the focus group discussion and observation will be ordered, reduced and coded according to the qualitative data analysis method (Applied health Research Manual: Anthropology of Health & Medical Care: report- International Congress in Anthropology of Health and Health care). All sorts of qualitative data will be summarized and a detailed report will be presented. Emphasis will be given on change of KAP (Knowledge, attitude and practice), BCC (Behavior change communication) among the participants. Statements about various important issues and graphical presentation of the reason behind the issues and socio-economic cycle behind the important issues will be presented. Matrix, diagram and flow chart will be presented as the reason / origin (both socio-economical and bio-medical) behind malnutrition, failure to improve nutritional status by the study subjects. Conclusion will be drawn based on the data, matrix, diagram and flow chart and possible causes will be explained. Recommendations will also be given on this connection. The qualitative data will help mainly to explain in-depth believes and thoughts behind food and health behavior and will identify changed perceptions on BCC. This information will explain more the process of change to link with frequency of performance or absolute terms of weight gain or improvement of nutritional status. Qualitative data will help to identify the cultural background of nutrition that will be employed in developing curriculum/package of nutrition education.

Investigators experience

The investigators will be from ICDDR, B and BRAC that will help operation of the project. The investigators are experienced with recently completed operations research project on "Effective means to address moderately malnourished children", BINP community based nutrition component (CBNC) and knowledgeable on the current operation at the Thana level. The experience on requirement and effectiveness of training components of intensive nutrition education will guide the most economic way to find the feasible means. The collaboration with BINP and partner NGOs includes assistance in training, and IEC distribution, organization of local support groups, regular monitoring and quality control.

Ethical Assurance for Protection of Human Rights

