
ensuring child caring practices. Data on morbidity will be collected and necessary medical advice for referral to the health centre will be given equally to each group. The CNP and CNO's time will be mapped and will be asked to adopt study messages to examine the practicality. Data collection, counseling on child caring practice, food demonstration and nutrition education using IEC will be organized and supervised by project staff. It is assumed that if the intervention is successful, and once the nutritional status improves, they are likely to maintain good health. The IEC on dietary practice will be communicated to the VNMC (village nutrition management committee) members for further preventive measures. Data on cost effectiveness of the nutrition education strategies will be collected by a health economist. Data will be analyzed for change in nutritional status from moderate to mild malnutrition or normal nutrition and proportions of children continuing complementary feeding will be compared between the intensive and less intensive intervention and control groups. It is expected that the results of the study will help define the effectiveness of our nutrition education package to prevent and reduce moderate malnutrition existing in large proportion of children in setting with different geographical, and cultural and feeding practices.

KEY PERSONNEL (List names of all investigators including PI and their respective specialties)

Name	Professional Discipline/ Specialty	Role in the Project
1. [name]	Scientist, ICDDR, B	Principal Investigator
2. [name]	Director, CSD, ICDDR,B	Co-Principal Investigator
3. [name]	Senior Medical officer ICDDR, B	Co-Investigator
4. [name]	BRAC, Bangladesh	Collaborative investigator

DESCRIPTION OF THE RESEARCH PROJECT

Hypothesis to be tested:

Concisely list in order, in the space provided the hypothesis to be tested and the Specific Aims of the proposed study. Provide the scientific basis of the hypothesis, critically examining the observations leading to the formulation of the hypothesis.

Hypothesis

- a. Less intensive nutrition education including food demonstration at the community level will be equally effective as intensive nutrition education for the prevention and reduction of moderate malnutrition.
- b. The effect of less intensive nutrition education given over a period of 6 months will sustain during the following six months without any intervention.

Specific Aims:

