The Government aims to establish an effective national nutrition program to improve child survival, strengthen the demand of services, prevention of malnutrition in children, improve low birth weight, increase learning capability of children, to have healthier and more productive future generation.

Results from the initial study at Shahrasti:

In the BINP project there was a recognition that a very large proportion of under two children are moderately malnourished. Yet experience compared to intervention severe malnourished children there was no definitive intervention to improve the situation in moderately malnourished children, as there was little worldwide successful. Therefore an operations research was commissioned by BINP to investigate effective means to address moderately malnourished children (weight for age between 60-75% median NCHS standard). Care givers of one group received intensive nutrition education (INE) for three months, the second group received intensive nutrition education plus daily 300 Kcal food supplementation (SF) of BINP (INE+ SF), and the third group as control received the standard BINP intervention of two weekly education by the implementing NGO CNP's. The study subjects were observed for an additional period of three months after intervention. Significant improvement in nutritional status was evident with intensive nutrition education in 3 months. The results show that the nutrition education reduced 37% of moderate malnutrition, whereas added with food supplements, nutrition education reduced 47% and there was 18% reduction in the control

group. Net weight gains (g) over the three months intervention period were 436 Vs 320, 688 Vs 334, 910 Vs 636 grams at the end of the 1st month, 2nd month and 3rd month of intervention in education Vs control group. The weight of the group receiving both supplementation and education were even higher i. e 487g at 1st month, 763g at 2nd month and 1061g at 3rd month respectively. The rates of weight gains (g/kg BW) in 3 months were 104g, 154g and 182g in control, education and SF+ education group respectively.

Substantially greater reduction of moderately malnourished children indicates the potential of intensive education and education plus SF for reduction of childhood malnutrition.

(Detail results of Shahrasti field project given in the Annex 3, page –42.)

Current state of nutrition

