In each CNC about 20 children are expected to suffer from moderate malnutrition.

The study hypothesis is that there will be no difference in improvement between intensive nutrition education group and less intensive education group in proportions improving from moderate malnutrition receiving nutrition education. The study will disprove the hypothesis if a 15% difference is detected with statistical significance.

$$\text{Using formula } n = \frac{p_1(1-p_1) + p_2(1-p_2)}{(p_1 - p_2)^2} (z_{\alpha} + z_{\beta})^2$$

(Reference: G W Snedecor and WG Cockran. Statistical Methods in Medical sciences. Oxford Publications 6th edition 1968, pp 111-114). Where p_1 is proportion of reduction of moderate malnutrition in intensive nutrition intervention group and p_2 is reduction in proportion of malnutrition in less intensive education group and $(z_{\alpha} + z_{\beta})$ is the function of level of significance and power of the statistical test.

$p_1=0.5$ and $p_2=0.35$

where z_{α} = level of significance at 5%, =1.96

and z_{β} = power of the study 90%, =1.28

where $(p_1 - p_2)$ = difference of proportion moving to mild malnutrition between control and intervention group.

$$n = \frac{0.5 \times 0.5 + 0.35 \times 0.65}{(0.15)^2} \times 10.5 = 222.$$

Taking a cluster effect of the design as the children will be selected from CNC s this is increased to $222 \times 1.5 = 333$. with a drop out possibility of 10%, it will be about 366 children in each group.

Total sample size will be $366 \times 2 = 732$ or 750 subjects.

Sample size for preventive study group:

Assumption is that mildly malnourished children will usually slip into moderate malnutrition without any nutrition education but with less intensive nutrition education, they will not slip into malnutrition. The study will be interested to detect a difference of 20% with a 5% probability and

90% power.

[figure not shown]
To detect this 20% difference the number of mildly malnourished children in two study groups will be $(121 \times 2) = 242$. The cluster effect of randomization by CNCs will be controlled by multiplying the number by a factor of 1.5 i.e. $242 \times 1.5 = 363$ for mildly malnourished groups and possible drop out (10%) can be covered with a total number of $(190 \times 2) = 380$ subjects.

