Data collection on anthropometry e.g. weight, length and mid upper arm circumference was done by the health assistants at two weekly intervals, morbidity at weekly interval, food intake and feeding practices at weekly intervals on pre-designed questionnaire. Point prevalence survey was conducted to find the practices of mothers on child feeding behavior. The study subjects were followed up for observation for a period of three months in absence of intervention.

There was significant improvement in nutritional status with intensive nutrition education in three months time. The results show that the nutrition and other education reduced 56% of moderate malnutrition, supplementary feeding and nutrition education reduced 64% and there was 30% reduction in the control group.

Net weight gain (grams) over three month's of intervention was 436 Vs 320, 688 Vs 334, 910 Vs 636 grams at one month, 2 months, and 3 months of intervention in education Vs control group respectively. The weight gain in group receiving both supplementation and education was even grater, 487g at 1 month, 763g at 2 month, and 1061g at three month respectively. The rate of weight gain in 3 months was 104, 154 and 182 g/kg in control, education and SF+ education group respectively ($p < 0.001$). There was substantial improvement in complementary feeding frequency (average 5.3 from 2.5 times per day) associated with nutrition education compared with the control group.

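### The hypothesis that less intensive education is as effective as intensive education is judged by a difference test with no margin, so a non-significant result could be read as equality

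*Protocol*

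**What the plan says.** Protocol, Hypothesis, item a: "Less intensive nutrition education including food demonstration at the community level will be equally effective as intensive nutrition education".

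Protocol, Sample size for management study group: "The study hypothesis is that there will be no difference in improvement between intensive nutrition education group and less intensive education group". The rule follows: "The study will disprove the hypothesis if a 15% difference is detected with statistical significance". The calculation takes 50% improving with INE and 35% with LINE, with "level of significance at 5%, =1.96" and "power of the study 90%, =1.28". It arrives at 222 per group, 333 after a cluster factor of 1.5, and 366 after 10% dropout. The planned number is 375 per group, 750 in all.

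Protocol, Data Analysis: t tests or non-parametric tests, chi-squared tests for categorical variables, and multiple regression on weight gain. On timing it says: "Separate analysis will be performed for periods of intervention, reinforcement and observation". The protocol contains no equivalence or non-inferiority margin and no confidence-interval criterion.

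The earlier Shahrasti study is reported twice. The Background says "the nutrition education reduced 37% of moderate malnutrition", against 18% in the control group. Annexure 4 says "the nutrition and other education reduced 56% of moderate malnutrition", against 30% in the control group.

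**The concern.** The claim the trial hopes to make is placed in the null hypothesis. A difference test can reject that null but cannot establish it. The protocol says what would disprove the hypothesis, not what would support it, and it provides no inconclusive outcome.

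Influences that shrink the observed gap favour the hoped-for answer. The five education centres in each union are divided between INE and LINE, one health assistant covers three centres, and Annexure 4 reports that workers in the earlier control area adopted the study's messages.

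The stakes are high. Annexure 1 says LINE is being tested with a view to nationwide replication, and the dissemination section says the national nutrition programme will use the results at once.

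**Working it through.** **Inputs.** INE 0.50 and LINE 0.35, two-sided 5% (z = 1.96), 90% power (z = 1.28), cluster factor 1.5 and 10% dropout (management sample size); 375 per group (selection and randomization section). The margins below are assumptions, because the protocol states none.

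**1. The protocol's own figure.** n = (0.50×0.50 + 0.35×0.65) / 0.15² × 10.5 = 0.4775 / 0.0225 × 10.5 = 222.8 (stated 222). Then 222 × 1.5 = 333 and 333 × 1.1 = 366.3 (stated 366). The arithmetic is sound, as a calculation for detecting a difference.

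**2. Effective size.** 375 × 0.9 / 1.5 = 225 per arm.

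**3. Chance that the planned test is non-significant when LINE is truly worse.** With INE at 50%, SE = √[(0.25 + p₂(1−p₂)) / 225] and P(non-significant) ≈ 1 − Φ(deficit/SE − 1.96).

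| True deficit | SE | Deficit/SE | P(non-significant) |
|---|---|---|---|
| 5 points | 0.0470 | 1.063 | about 81% |
| 7.5 points | 0.0469 | 1.600 | about 64% |
| 10 points | 0.0467 | 2.143 | about 43% |
| 15 points | 0.0461 | 3.256 | about 10% |

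A pooled-variance calculation with 222 per arm gives 82%, 65%, 44% and 11%. The 95% half-width is about 9 points (1.96 × 0.0467 = 0.0915), so observed gaps up to about 9 points would leave the hypothesis standing.

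**4. The same children under a non-inferiority rule.** Power = Φ[(margin − true deficit)/SE − 1.96], with 225 per arm.

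- Margin 15, both arms 50%: SE = √(0.50/225) = 0.0471; 0.15/0.0471 − 1.96 = 1.22; power 89%.
- Margin 15, both arms 35%: SE = √(0.455/225) = 0.0450; 0.15/0.0450 − 1.96 = 1.38; power 92%.
- Margin 15, LINE truly 5 points worse (50% v 45%): 0.10/0.0470 − 1.96 = 0.17; power 57%.
- Margin 10, arms equal: 56% (both 50%) to 60% (both 35%).

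For 90% power with both arms at 50%, a cluster factor of 1.5 and 10% loss, a 15-point margin needs 390 per group and a 10-point margin 877 per group.

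**5. What 15 points would concede.** The earlier INE effect over standard BINP education is 37 − 18 = 19 points (Background) or 56 − 30 = 26 points (Annexure 4). A 15-point loss gives up 15/19 = 79% or 15/26 = 58% of it.

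**The case against.** Three stronger readings are tempting, and the documents do not support them.

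- A reader might infer that the protocol treats non-significance as proof of equality. It does not say so. It says only what would disprove the hypothesis; the rest is inference from having that rule and no other.
- A reader might infer that the risk of a wrong verdict is uncontrolled. At the designed 15-point deficit it is held to about 10%. The weakness lies at smaller deficits.
- A reader might take the rule to require an observed gap of at least 15 points, which would catch a true 15-point deficit only about half the time. The sentence introduces a standard power formula and is better read as ordinary sample-size wording.

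On the remedy, the protocol offers 15 points as a detectable difference, not as an acceptable loss. Adopting it as a margin without comment would endorse a figure that is large beside the earlier effect. This stands, so the margin needs its own justification. It is also fair that the 19- and 26-point effects are imperfect yardsticks: they come from a three-month intervention, against a control group that picked up study messages, with flood recovery and harvest affecting all groups.

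The possible existence of a statistical analysis plan does not answer the point, because the protocol fixes both the hypothesis and the rule.

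**Conclusion.** The concern holds in this limited form. The stated rule cannot support the stated hypothesis, and it leaves that hypothesis standing in about 43% of trials when LINE is 10 points worse and about 81% when it is 5 points worse. These figures assume INE at 50%, the protocol's cluster factor of 1.5 and 10% loss.

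The planned size is not in itself the fault. Of the margins examined, 15 points is the only one that 750 children support at close to the intended 90% power, and only if the arms are truly equal. Such a result would show that LINE is not worse by 15 points or more. It would not show equal effectiveness.

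**What to change.** 1. Delete the sentence on disproving the hypothesis. Restate hypothesis a, for the management comparison, as non-inferiority of LINE to INE on the proportion leaving Grade II at the end of the 6-month intervention.
2. Conclude that LINE is not worse only if the upper limit of the two-sided 95% cluster-adjusted confidence interval for INE minus LINE lies below a prespecified, justified margin. Otherwise call the result inconclusive.
3. If 15 points is kept as the margin, say that it would concede 15 of 19 or 15 of 26 points of the earlier three-month effect over standard BINP education, and word the claim as not worse by 15 points or more. Reconcile the 37%/18% and 56%/30% reports.
4. If a stricter margin is chosen, state the lower power at the planned size (about 56% to 60% for 10 points) or recompute the number of children.

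Cost: with a 15-point margin, wording only. The 750 children stay, and power is stated as about 89% to 92% with arms truly equal and about 57% with LINE 5 points worse. A stricter margin costs either power or more children. The new rule deals with sampling error only; mixing of the two packages between neighbouring centres would still narrow the gap and has to be limited in the conduct of the trial.
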